3.2 Exclusion Criteria

- Prior treatment with regorafenib.
- Previous assignment to treatment during this study. Subjects permanently withdrawn from study participation will not be allowed to re-enter study.
- Uncontrolled hypertension (systolic pressure >140 mm Hg or diastolic pressure > 90 mm Hg [NCI-CTCAE v4.0] on repeated measurement) despite optimal medical management.
- Active or clinically significant cardiac disease including:
 - o Congestive heart failure New York Heart Association (NYHA) > Class II.
 - Active coronary artery disease.
 - o Cardiac arrhythmias requiring anti-arrhythmic therapy other than beta blockers or digoxin.
 - O Unstable angina (anginal symptoms at rest), new-onset angina within 3 months before randomization, or myocardial infarction within 6 months before randomization.
- Evidence or history of bleeding diathesis or coagulopathy.
- Any hemorrhage or bleeding event: NCI CTCAE v4.0 Grade 3 within 4 weeks prior to study registration.
- Subjects with thrombotic, embolic, venous, or arterial events, such as cerebrovascular accident (including transient ischemic attacks) deep vein thrombosis or pulmonary embolism within 6 months prior to study registration.
- Subjects with any previously untreated or concurrent cancer that is distinct in primary site or histology except cervical cancer in-situ, treated basal cell carcinoma, or superficial bladder

tumor. Subjects surviving a cancer that was curatively treated and without evidence of disease for more than 3 years before registration are allowed. All cancer treatments must be completed at least 3 years prior to study registration.

- Patients with pheochromocytoma.
- Known history of human immunodeficiency virus (HIV) infection or current chronic or active hepatitis B or C infection requiring treatment with antiviral therapy.
- Ongoing infection > Grade 2 NCI-CTCAE v4.0.
- Symptomatic metastatic brain or meningeal tumors.
- Presence of a non-healing wound, or non-healing ulcer, (that is not tumor related) or bone fracture.
- Major surgical procedure or significant traumatic injury within 28 days prior to study registration.
- Other investigational treatment during or within 4 weeks prior to study registration.
- Use of any approved tyrosine kinase inhibitors within 2 weeks or 6 half-lives of the agent, whichever is shorter, prior to study registration.
- Prior radiation within 14 days prior to study registration.
- Renal failure requiring hemo-or peritoneal dialysis.
- Dehydration Grade ≥1 NCI-CTCAE v4.0.
- Patients with seizure disorder requiring medication.
- Persistent proteinuria > Grade 3 NCI-CTCAE v4.0
- Interstitial lung disease with ongoing signs and symptoms at the time of informed consent.
- Pleural effusion or ascites that causes respiratory compromise (2: NCI-CTCAE version 4.0 Grade 2 dyspnea).
- History of organ allograft (including corneal transplant).
- Known or suspected allergy or hypersensitivity to any of the study drugs, study drug classes, or excipients of the formulations given during the course of this trial.
- Any malabsorption condition.
- Women who are pregnant or breast-feeding.
- Any condition which, in the investigator's opinion, makes the subject unsuitable for trial participation.
- Substance abuse, medical, psychological or social conditions that may interfere with the subject's participation in the study or evaluation of the study results.

3.3 Excluded therapies and medications, previous and concomitant

- Concurrent anti-cancer therapy (chemotherapy, radiation therapy, surgery, immunotherapy, biologic therapy, or tumor embolization) other than study treatment (regorafenib, other agents being investigated in combination with regorafenib).
- Prior use of regorafenib.

Concurrent use of another investigational drug or device therapy (i.e., outside of study treatment) during, or within 4 weeks prior to study registration. Subjects are allowed to participate in trials involving investigational agents used for the treatment of PPE symptoms.

- •
- Major surgical procedure, open biopsy, or significant traumatic injury within 28 days before start of study medication.
- Therapeutic anticoagulation with Vitamin-K antagonists (e.g., warfarin) or with heparins and

heparinoids.

- o However, prophylactic anticoagulation as described below is allowed:
 - Low dose warfarin (1 mg orally, once daily) with PT-INR ≤ 1.5 x ULN is permitted. Infrequent bleeding or elevations in PT-INR have been reported in some subjects taking warfarin while on regorafenib therapy. Therefore, subjects taking concomitant warfarin should be monitored regularly for changes in PT, PT-INR or clinical bleeding episodes.
 - Low dose aspirin (≤ 100 mg daily).
 - Prophylactic doses of heparin.
- Use of any herbal remedy (e.g. St. John's Wort [Hypericum perforatum])

3.4 Inclusion of Women and Minorities

Both men and women of all races and ethnic groups are eligible for this trial.

4. REGISTRATION PROCEDURES

4.1 General Guidelines for DF/HCC and DF/PCC Institutions

Institutions will register eligible participants in the Clinical Trials Management System (CTMS) OnCore. Registrations must occur prior to the initiation of protocol therapy. Any participant not registered to the protocol before protocol therapy begins will be considered ineligible and registration will be denied. An investigator will confirm eligibility criteria and a member of the study team will complete the protocol-specific eligibility checklist.

Following registration, participants may begin protocol therapy. Issues that would cause treatment delays should be discussed with the Overall Principal Investigator (PI), [name]. If a participant does not receive protocol therapy following registration, the participant's registration on the study must be canceled. Registration cancellations must be made in OnCore as soon as possible.

4.2 Registration Process for DF/HCC and DF/PCC Institutions

DF/HCC Standard Operating Procedure for Human Subject Research Titled *Subject Protocol Registration* (SOP #: REGIST-101) must be followed.

4.3 General Guidelines for Other Investigative Sites

Eligible participants will be entered on study centrally at Dana-Farber Cancer Institute by the Study Coordinator. All sites should call the Study Coordinator to verify dose level availabilities. Following registration, participants should begin protocol therapy within 5 days.

Issues that would cause treatment delays should be discussed with the Overall PI. If a participant does not receive protocol therapy following registration, the participant's registration on the study must be canceled. The Study Coordinator should be notified of cancellations as soon as possible.

4.4 Registration Process for Other Investigative Sites

To register a participant, the following documents should be completed by the research nurse or data manager and faxed or e-mailed to the Study Coordinator:

• Copy of required laboratory tests, please refer to section 10.

- Signed participant consent form
- HIPAA authorization form
- Eligibility checklist completed by the treating physician, assistant, nurse practitioner, and/or registered nurse.

The research nurse or data manager at the participating site will then call or e-mail the Study Coordinator to verify eligibility. To complete the registration process, the Coordinator will follow DF/HCC Standard Operating Procedure for Human Subject Research Titled *Subject Protocol Registration* (SOP #: REGIST-101) and register the participant on the protocol. The coordinator will fax or e-mail the participant study number, and if applicable the dose treatment level, to the participating site. The coordinator will also call the research nurse or data manager at the participating site and verbally confirm registration

5. TREATMENT PLAN

5.1 Treatment Regimen

Regorafenib will be administered as monotherapy during the study. Subjects will take one dose daily for 3 weeks on /1 week off. One cycle is 28 days.

During cycle 1, patients will start taking 80mg for one week. If no significant drug related toxicities (SDRT's) occur, the dose will be escalated to 120mg daily starting day8. If no SCRT's occur, the dose will be escalated to 160mg daily.

From cycle 2 onward, the highest tolerated dose will be the treatment dose level.

Dose Escalation Plan:

Cycle	Week	Daily Dose	
Cycle 1	Week 1	80 mg	Two 40-mg tablets of regorafenib
	Week 2	120 mg	Three 40-mg tablets of regorafenib
	Week 3	160 mg	Four 40-mg tablets of regorafenib
	Week 4	No dosing	
Cycle 2-onwards	Week 1-3	Highest tolerated dose	
	Week 4	No dosing	

Regorafenib tablets should be taken once a day with approximately 8 fluid ounces (240 mL) of water after a low-fat (<30% fat) meal. Some examples of lowfat meals are:

- Two slices of white toast with 1 tablespoon of low-fat margarine and 1 tablespoon of jelly and 8 ounces (240 mL) of skim milk (approximately 319 calories and 8.2 g of fat).
- One cup of cereal (i.e. Special K), 8 ounces (240 mL) of skim milk, one piece of toast with jam (no butter or marmalade), apple juice, and one cup of coffee or tea (2 g fat, 17 g protein, 93 g of carbohydrate, 520 calories.

5.2 Agent Administration

Regorafenib tablets will be packaged in high density polyethylene bottles with a white child resistant closure and induction seal. Each bottle includes 28 tablets and a 3-gram desiccant. The bottles will have a label affixed containing study identification, product identification, and quantity

of tablets. Once the drug has been received it must be kept in a secure, dry location. Study drug must be stored in its original bottle at a temperature not above 25°C (77°F).

The study drug must be exclusively used for the investigation specified in this protocol and it will only be accessible to authorized staff.

5.3 Drug logistics and accountability

All study drugs will be stored at the investigational site in accordance with Good Clinical Practice (GCP) and Good Manufacturing Practices (GMP) requirements and the instructions given by the clinical supplies department of the Institution and will be inaccessible to unauthorized personnel.

5.3.1 **Accountability**

The investigator, or a responsible party designated by the investigator, must maintain a careful record of the inventory and disposition of the agent (investigational or free of charge) using the NCI Drug Accountability Record or another comparable drug accountability form. (See the CTEP website at http://ctep.cancer.gov/ProtocolDevelopment for the "Policy and Guidelines for Accountability and Storage of Investigational Agents" or to obtain a copy of the drug accountability form.)

5.3.2 **Destruction and Return**

At the end of the study, unused supplies of regorafenib should be destroyed according to institutional policies. Destruction will be documented in the Drug Accountability Record Form. The certificate of destruction should be sent to Bayer.

A completed "Unused Study Drug Disposition Form Destruction or Return Confirmation" should be sent to Bayer at the following address:

E-mail: OR

Mail: (VP of Medical Affairs named in contract) at Bayer HealthCare Pharmaceuticals [name]

5.4 Treatment compliance

An adequate record of receipt, distribution, and return of the study drug must be kept on the NCI Drug Accountability Form.

Subject compliance with the treatment and protocol includes willingness to comply with all aspects of the protocol, and to have blood collected for all safety evaluations. At the discretion of the principal investigator, a subject may be discontinued from the trial for non-compliance with follow-up visits or study drug.

5.5 Prior and concomitant therapy

All medication that is considered necessary for the subject's welfare, and which is not expected to interfere with the evaluation of the study treatment, may be given at the discretion of the investigator. All medications (including contrast media) taken within 2 weeks prior to the start of the study and during the study must be recorded in the subject's source documentation and in the CRF (including start/stop dates, dose frequency, route of administration, and indication). Specific caution should be taken when considering or administering a concomitant medication that is metabolized

by the cytochrome enzymes CYP2C8, CYP2B6 and CYP2C9. Such concomitant medication should be avoided, if possible.

Co-administration of a strong CYP3A4 inducer (rifampin) with a single 160 mg dose of regorafenib decreased the mean exposure of regorafenib, increased the mean exposure of the active metabolite M-5, and resulted in no change in the mean exposure of the active metabolite M-2. Avoid concomitant use of regorafenib with strong CYP3A4 inducers (e.g. rifampin, phenytoin, carbamazepine, phenobarbital, and St. John's Wort).

Co- administration of a strongCYP3A4 inhibitor (ketoconazole) with a single 160mg dose of regorafenib increased the mean exposure of regorafenib and decreased the mean exposure of the active metabolites M-2 and M-5. Avoid concomitant use of regorafenib with strong inhibitors of CYP3A4 activity (e.g. clarithromycin, grapefruit juice, itraconazole, ketoconazole, nefazadone, posaconazole, telithromycin, and voriconazole).

5.6 Permitted concomitant therapy includes:

- Standard therapies for concurrent medical conditions.
- Supportive care for any underlying illness.
- Palliative radiation therapy is allowed if the target lesion(s) are not included within the radiation field and no more than 10% of the bone marrow is irradiated.
- Granulocyte colony-stimulating factor (G-CSF) and other hematopoietic growth factors may be used in the management of acute toxicity, such as febrile neutropenia, when clinically indicated or at the investigator's discretion. However, they may not be substituted for a required dose reduction. Subjects are permitted to take chronic erythropoietin.
- Treatment with nonconventional therapies (such as acupuncture), and vitamin/mineral supplements are permitted provided that they do not interfere with the study endpoints, in the opinion of the investigator.
- Bisphosphonates
- Subjects who are prophylactically treated with an agent such as warfarin or heparin will be allowed to participate provided that their medication dose and INR/PTT are stable. Close monitoring (day 5 of cycle 1 and day 1 of each cycle) is mandatory. If either of these values are above the therapeutic range, the doses should be modified and the assessments should be repeated weekly until they are stable.

5.7 The following are not permitted:

- Other investigational treatment during or within 30 days before starting study treatment
- Systemic antitumor therapy, including cytotoxic therapy, signal transduction inhibitors, immunotherapy, and hormonal therapy
- Bone marrow transplant or stem cell rescue
- Subjects taking narrow therapeutic index medications should be monitored proactively (e.g. warfarin, phenytoin, quinidine, carbamazepine, Phenobarbital, cyclosporin, and digoxin). Warfarin is metabolized by the cytochrome enzyme CYP2C9 and its levels may be especially affected by regorafenib
- Use of any herbal remedy (e.g. St. John's Wort [Hypericum perforatum])

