3. PARTICIPANT SELECTION

3.1 Inclusion Criteria

- Subjects must be able to understand and be willing to sign the written informed consent form.
 A signed informed consent form must be appropriately obtained prior to the conduct of any trial-specific procedure.
- Age≥18 years.
- Eastern Cooperative Oncology Group performance status of ≤ 1 .
- Histologically or cytologically confirmed diagnosis of metastatic medullary thyroid cancer or histologically or cytologically confirmed diagnosis of RAI refractory differentiated thyroid cancer for which no curative treatment option exists.
- Documented disease progression as defined by RECIST criteria within 6 to 12 months prior to study registration for patients with MTC and within 12 months prior to study registration for patients with RAI refractory DTC.
- Must have at least 1 site of measurable disease by RECIST criteria, by version 1.1.
- Archival tissue block or unstained slides (from primary or metastatic site) must be available, otherwise fresh tissue biopsy sample will be collected for patients with accessible tumors.
- Any number of prior chemotherapies and targeted therapies are allowed.

- Adequate bone marrow, liver and renal function as assessed by the following laboratory requirements within 3 weeks prior to study registration:
 - Total bilirubin: ≤ 1.5 x the upper limits of normal (ULN)
 - Alanine aminotransferase (ALT) and aspartate amino-transferease (AST): $\leq 2.5 \text{ x ULN}$ (: $\leq 5 \text{ x ULN}$ for subjects with liver involvement of their cancer)
 - O Alkaline phosphastase limit: $\leq 2.5 \text{ x ULN}$ (: $\leq 5 \text{ x ULN}$ for subjects with liver involvement of their cancer)
 - o Serum creatinine: < 1.5 x the ULN
 - o International normalized ratio (INR)/ Partial thromboplastin time (PTT): ≤ 1.5 x ULN. (Subjects who are prophylactically treated with an agent such as warfarin or heparin will be allowed to participate provided that no prior evidence of underlying abnormality in coagulation parameters exists. Close monitoring of at least weekly evaluations will be performed until INR/PTT is stable based on a measurement that is pre-dose as defined by the local standard of care. (See Section 3.3)
 - Platelet count \geq 100000 /mm3, hemoglobin (Hb) \geq 9 g/dL, absolute neutrophil count (ANC) \geq 1500/mm3. Blood transfusion to meet the inclusion criteria will not be allowed.

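### Section 5.6 triggers action on INR only above a therapeutic range, but section 3.3 leaves warfarin patients with no such range and caps PT-INR at 1.5 × ULN

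*Combined protocol and SAP*

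**What the plan says.** The rules for prophylactic anticoagulants are spread over several sections of the combined protocol and SAP.

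- **Section 3.3** excludes anticoagulation at therapeutic intensity, whether by vitamin-K antagonist or by heparin. Among its exceptions for prophylaxis: "Low dose warfarin (1 mg orally, once daily) with PT-INR ≤ 1.5 x ULN is permitted". It then gives the hazard: "Infrequent bleeding or elevations in PT-INR have been reported in some subjects taking warfarin while on regorafenib therapy". It asks for regular checks of PT, PT-INR and bleeding in warfarin patients, with no interval and no action limit.
- **Section 5.6** admits prophylactically treated patients "provided that their medication dose and INR/PTT are stable". It continues: "Close monitoring (day 5 of cycle 1 and day 1 of each cycle) is mandatory". The action rule follows: "If either of these values are above the therapeutic range, the doses should be modified and the assessments should be repeated weekly" until stable.
- **Section 3.1** sets an entry limit for INR/PTT of 1.5 × ULN and, for prophylactic patients, says "Close monitoring of at least weekly evaluations will be performed until INR/PTT is stable based on a measurement that is pre-dose".
- **Section 5.5** says of drugs metabolised by CYP2C8, CYP2B6 and CYP2C9: "Such concomitant medication should be avoided, if possible". Section 5.7 names warfarin as a CYP2C9 drug that regorafenib may affect.
- **Section 10 (Study Calendar), footnote a** places INR, PT and PTT in the serum chemistry row.

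**The concern.** Sections 3.3 and 5.6 deal with the same patients but use different yardsticks. Section 3.3 defines what is acceptable for warfarin by a multiple of the normal limit. Section 5.6 defines when to act by reference to a range that belongs to patients who are deliberately anticoagulated, and 3.3 keeps those patients out of the trial. The only sentence that tells a site to do something about a raised INR is thus tied to a threshold that its own population does not have.

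What is at stake is patient safety in a small subgroup. A patient whose PT-INR rises past the 3.3 limit on treatment could stay on warfarin, with no dose change and no weekly repeats, at a site that follows 5.6 as written. The protocol already recognises the interaction as a bleeding hazard.

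**Working it through.** No design figure is involved, so the check compares the sections.

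**Inputs.** Limit in 3.3: PT-INR ≤ 1.5 × ULN, at a fixed warfarin dose of 1 mg daily. Trigger in 5.6: a value above U, where U is the upper end of a therapeutic range. The documents give no value for U.

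**Step 1: apply both rules to a PT-INR reading in a patient on 1 mg warfarin.**

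| Reading | Section 3.3 | Section 5.6 |
|---|---|---|
| ≤ 1.5 × ULN | permitted | no action |
| > 1.5 × ULN but ≤ U | outside the permitted use | no action |
| > U | outside the permitted use | modify dose, repeat weekly |

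The middle row is the gap. It is empty only if U is taken to equal 1.5 × ULN, and nothing in the documents says so.

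**Step 2: look for another on-study action limit that would fill the middle row.**

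- Section 3.1 gives an entry limit and weekly checks until stable. It does not say what to do with a high value.
- Section 3.3 asks for regular monitoring, with no threshold for action.
- Section 5.7 asks for proactive monitoring of narrow-therapeutic-index drugs, including warfarin, again with no threshold.
- Sections 7.1 and 7.5 ask for monitoring after regorafenib dose selection or modification, by local standard of care, with no threshold.
- Table 1 in section 6 adjusts regorafenib, not warfarin. It makes no change at grades 0 to 2, and its footnote b sets aside asymptomatic laboratory abnormalities.

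None of these supplies an action limit for PT-INR during treatment.

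**Step 3: what a dose modification can mean.** Section 5.6 does not say which drug's dose is changed. Since it has just spoken of the patient's anticoagulant dose, that is the natural reading. With warfarin permitted only at 1 mg daily, the change can only be a reduction or a hold. The fix should say so.

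**The case against.** The best counter-argument is that the two sections should be read together. Section 3.3 is headed as covering both previous and concomitant medication. If its limit applies throughout treatment, warfarin above 1.5 × ULN is no longer permitted whatever 5.6 says. If it applies only at entry, there is no on-treatment limit for 5.6 to contradict. Either way, the argument runs, only a cross-reference is missing.

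This narrows the point but does not remove it. On the first reading, 3.3 does not say what the site should do, and the section that does say so uses a different threshold. On the second, the only on-treatment trigger still refers to a range that these patients do not have.

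It is also fair to say that a careful site may take the range for a 1 mg patient to be the one permitted in 3.3. At such a site there is no gap, and the fix only writes down existing practice.

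The same phrase in 5.6 also governs PTT in patients on prophylactic heparin. That observation stands. However, 3.3 attaches no PTT limit to prophylactic heparin, so it offers no figure to insert, and the point is confined to warfarin.

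**Conclusion.** The trigger in section 5.6 does not fit the patients it governs and should be aligned with section 3.3. This is a minor point. It rests on the text alone and needs no assumption about INR values. The number of patients on 1 mg warfarin is not stated; 0 to 2 of the 22 DTC patients in section 13.1 is an assumption, and zero is possible. The response-rate design, the endpoints and the sample size are unaffected.

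A reader might infer two stronger claims. The documents support neither.

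- **A numerical width for the gap.** Assume an INR ULN of 1.0 to 1.2 and a site range ending at 2.5 to 3.5. The band would then run from 2.5 − 1.5 × 1.2 = 0.7 to 3.5 − 1.5 × 1.0 = 2.0 INR units. Neither assumed range is in the documents, and the width is zero if a site uses the 3.3 limit. No width is claimed.
- **A defective INR schedule from cycle 3.** From cycle 3 the only scheduled INR before end of treatment is indeed on day 1, after the week off. With the 20 to 40 hour half-life in section 2.3.2, the parent drug would then be at 0.5^(168/20) = 0.3% to 0.5^(168/40) = 5.4% of its on-treatment trough. But the documents do not link INR to regorafenib level, the active metabolites are not in that calculation, and the ±3-day window can move the draw. INR is already read on drug at cycle 1 days 5, 8 and 15 and at cycle 2 day 15. Section 3.3 also asks for regular monitoring with no end date. Extra on-drug draws are a matter of preference, not a correction.

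The 5.7 monitoring instruction sits in a list of things not permitted. That is editorial.

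**What to change.** In section 5.6, for patients on warfarin, replace the reference to a therapeutic range with *PT-INR > 1.5 × ULN (see 3.3)*. State that the warfarin dose is then held or modified. Keep the weekly repeats until stable, the existing monitoring days and the section 3.1 rule. Leave the heparin/PTT wording as it is.

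The change is to text only. Its running cost is a few more repeat INRs in the few patients, possibly none, on 1 mg warfarin, because the lower trigger will be met more often. An additional on-drug INR from cycle 3 for warfarin patients is optional and is not part of this recommendation.
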